“Early Sodium Intake in Preterm Newborns; Randomized Clinical Trial”

NCT04035564

January 2018

Introduction

Hyponatremia is a common complication among preterm infants, renal losses of sodium contribute to the development of hyponatremia in preterm newborns. Sodium imbalances impact in newborns outcome. There is controversy about the time of initiation and the requirements of sodium in premature infants. Hypothesis: early (24 hours of life) sodium supplementation (5mEq/kg/day) prevents the develop of hyponatremia in preterm infants.

This study is a randomized controlled trial in infants less than 35 weeks gestation admitted to the Newborn Intensive Care Unit at Children Hospital in Saltillo Coahuila Mexico.

Infants receive at 24 hours of life; sodium (5mEq/kg/day) versus less than 1mEq/kg/day. Weight, serum and urine sodium, serum chloride, serum and urine creatinine, serum chloride, bicarbonate and glucose are monitored daily during the first 3 days of life. Patients are assessed for hyponatremia, hypernatremia, weight change, sepsis, necrotizing enterocolitis and intraventricular hemorrhage.

Objectives:

1. Compare the risk of hyponatremia in the first 72hrs of life, in preterm newborns with early sodium intake and late sodium intake.
2. Compare the risk of hypernatremia in the first 72hrs of life, in preterm newborns with early sodium intake and late sodium intake.
3. Assess the change in serum sodium in preterm newborns with early sodium intake and late sodium intake.
4. Assess the weight change in preterm newborns with early sodium intake and late sodium intake.
5. Assess the development of complications (sepsis, necrotizing enterocolitis, intraventricular hemorrhage, mortality) in preterm newborns with early sodium intake and late sodium intake.

Study design and statistical analysis

This study is a randomized controlled trial.

Eligibility criteria:

Preterm infants <35 weeks of gestation.

Less than 24 hours of life.

Exclusion criteria:

Urinary malformations
Congenital abdominal wall defect
Intestinal atresia / obstruction
Congenital heart defect

The eligible patients will be simple randomized in two groups:

1. Comparison: Sodium administration, enteral and/or parenteral less than 1mEq/kg/day starting on day of life one.
2. Intervention: Sodium administration, enteral and/or parenteral of 5mEq/kg/day starting on day of life one.

At admission, gestational age and sex and birth weight will be recorded. Weight will be evaluated every 24 hours for 3 days.

Blood samples will be taken every 24 hours for 3 days to assess serum sodium, creatinine, glucose, sodium bicarbonate and serum chloride levels.

Urine samples will be taken every 24 hours for 3 days to assess urine sodium and urine creatinine levels.

The incidence of hyponatremia, hypernatremia, change of serum sodium and weight change will be evaluated and compared between groups during this time frame (72hrs).

The patients will be following through hospital stay to record the development of sepsis, necrotizing enterocolitis, intraventricular hemorrhage and mortality.

The distribution of variables will be assessed with Shapiro Wilk test, normally distributed data will be compared with t test or Chi squared test and those with abnormal distribution with Mann-Whitney U test or Fisher exact test. The risk of hyponatremia and hypernatremia will be expressed using relative risk.

The change of serum sodium, creatinine, chloride, sodium bicarbonate, glucose levels and weight will be evaluated using repeated measures ANOVA or Kruskal-Wallis test depending on data distribution.

Exploratory analysis will include sodium balance (according to sodium intake and urinary excretion), urine output and total fluid administration.

IBM SPSS Statistics (IBM Corp. Released in 2013. IBM Statistics for Windows, Version 21.0. Armonk NY: IBM Corp.) will be used for statistical analysis. A p-value <0.05 will be considered statistically significant.

Definitions:

Hyponatremia: Serum sodium <130mEq/L

Hypernatremia: Serum sodium >150mEq/L

Change in serum sodium: The difference between serum sodium (at 48 and 72hrs) and initial serum sodium.

Weight change: The difference between weight (at 24, 48 and 72hrs) and birth weight.

Sepsis: Positive blood culture and/or 5 days of continuous antimicrobial therapy.

Necrotizing enterocolitis: Necrotizing enterocolitis according to Bell staging (II or grater).

Intraventricular hemorrhage: Bleeding into the brain's ventricular system (intracranial ultrasound).

Mortality: Death during hospitalization.

References

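### Infants already hyponatremic or hypernatremic before study sodium starts are counted in relative risks meant to show prevention or incidence

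*Combined protocol and SAP*

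**What the plan says.** The Introduction states the hypothesis that early "sodium supplementation (5mEq/kg/day) prevents the develop of hyponatremia in preterm infants".

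Eligibility criteria give two conditions: "Preterm infants <35 weeks of gestation" and "Less than 24 hours of life". There are four exclusions: "Urinary malformations", "Congenital abdominal wall defect", "Intestinal atresia / obstruction" and cardiac malformation. None concerns serum sodium.

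Definitions score the two sodium outcomes by the measured value alone: "Hyponatremia: Serum sodium <130mEq/L" and "Hypernatremia: Serum sodium >150mEq/L". Objectives 1 and 2 compare the risk of each over the first 72 hours of life. The section on study design and statistical analysis calls these outcomes incidence and expresses them as relative risks. Initial serum sodium appears only in Definitions, as the reference for the change at 48 and 72 hours. No section excludes, stratifies, adjusts for or separately analyses infants whose initial value is already outside 130 to 150 mEq/L.

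**The concern.** Hyponatremia cannot be prevented from developing in an infant who already has it. As written, such an infant is randomised and stays in the analysis of objective 1. If the initial sample counts, the infant is an event whatever the treatment does. If only later samples count, an infant who enters at 127 and measures 128 at 48 hours is scored as a case, and one who enters at 127 and has corrected by 48 hours is scored as a non-case. The first is persistence and the second is treatment of an existing abnormality; neither bears on prevention. Deciding which samples count therefore does not settle the matter without also defining who is at risk.

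The prevention hypothesis names hyponatremia only, but the hypernatremia count in objective 2 is affected in the same way. A relative risk for harm could be understated because some events were present before study sodium began. At stake is whether the two relative risks answer the questions the plan asks.

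**Working it through.** **Inputs.** From the documents: the limits 130 and 150 mEq/L, the 72-hour window, and relative risk as the effect measure. The documents give no event rates, sample size or share affected at entry, so there is no stated figure to reproduce. Every rate below is an assumption.

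**Formula.** Let q be the share abnormal at entry (equal by arm in expectation), p1 and p0 the risks of new onset in the 5 mEq/kg/day arm and the comparison arm, and s1 and s0 the shares of entry cases that end up counted as events. Then

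RR observed = [q·s1 + (1−q)·p1] / [q·s0 + (1−q)·p0].

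If the initial sample counts, s1 = s0 = 1 automatically. If only later samples count, s1 and s0 are the shares persisting and may differ.

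**Hyponatremia, all entry cases counted** (p1 = 0.15, p0 = 0.30, true RR 0.50):

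- q = 2%: (0.02 + 0.147)/(0.02 + 0.294) = 0.167/0.314 = 0.53
- q = 5%: (0.05 + 0.1425)/(0.05 + 0.285) = 0.1925/0.335 = 0.57
- q = 10%: (0.10 + 0.135)/(0.10 + 0.27) = 0.235/0.370 = 0.64

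The same formula at other control risks, still with a true RR of 0.50, gives 0.55, 0.60 and 0.68 for 10% versus 20%, and 0.52, 0.56 and 0.61 for 20% versus 40%.

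For 15% versus 30%, 80% power needs 121 per arm (two-sided 5%, 1:1; the plan states neither sidedness nor allocation ratio). At that size, power falls to 77%, 71% and 63% for q = 2%, 5% and 10%.

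**Equal but partial persistence.** With s1 = s0 = 0.5 and q = 10%: (0.05 + 0.135)/(0.05 + 0.27) = 0.185/0.320 = 0.58. The ratio is still pulled toward 1, but less.

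**Unequal persistence** (15% versus 30%, q = 10%, later samples only):

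- Half of entry cases correct in the sodium arm, none in the comparison arm: (0.05 + 0.135)/0.370 = 0.50. The two influences cancel.
- All correct in the sodium arm, none in the comparison arm: 0.135/0.370 = 0.36. Prevention is overstated.

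**Hypernatremia** (p1 = 0.10, p0 = 0.05, true RR 2.0, q = 3%):

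- All entry cases counted: (0.03 + 0.097)/(0.03 + 0.0485) = 0.127/0.0785 = 1.62
- Full persistence in the sodium arm, half in the comparison arm: 0.127/(0.015 + 0.0485) = 0.127/0.0635 = 2.0

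**Timing of the initial sample.** The Introduction starts study sodium at 24 hours of life, while the arm descriptions start it on day of life one. Samples are daily for 3 days. Weight change is defined at 24, 48 and 72 hours, but sodium change only at 48 and 72 hours against the initial value. This suggests an initial sample near 24 hours, but no section says so or places it relative to allocation or the first study sodium.

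**The case against.** A broad entry rule is a legitimate design choice. Objectives 1 and 2 compare risk in preterm newborns as randomised, and that comparison is valid for the mixed population because entry cases balance in expectation. This stands. A reader might infer that the randomised comparison is invalid, and the documents do not support that. What fails is the match between the comparison and a hypothesis of prevention.

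The word incidence in the analysis section could be read as new cases only. That is possible, but no rule makes it so, and the 72-hour window opens at birth, before study sodium.

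The size may be negligible: at 2% affected, the ratio moves only from 0.50 to 0.53, and the direction is not fixed once persistence differs by arm. Both points stand. A reader might infer that the relative risk is always diluted; the working shows that it need not be.

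The strongest objection concerns the remedy. It is tempting to require an initial sodium of 130 to 150 mEq/L at entry, on the ground that the test is already done. Infants must be under 24 hours old at entry, and the initial sample may fall near 24 hours, so an entry limit could need an earlier or additional draw. Nor do the documents show that the initial value precedes allocation. If it follows the start of study sodium, restricting the analysis on it would select on a value that treatment may have changed. This stands and shapes the fix.

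**Conclusion.** The concern holds as a mismatch between the stated hypothesis and the infants counted. The absence of any sodium condition at entry and the value-only definitions are plain in the text. The numerical consequence is illustrative: 0.50 becomes about 0.53, 0.57 or 0.64 at 2%, 5% or 10% affected at entry, assuming 15% versus 30% and every entry case counted in both arms. With unequal correction by arm, the error can go in either direction. The true share affected at entry is unknown.

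A reader might also infer that randomising infants already above 150 mEq/L is itself an error. The documents do not settle that. They leave entry open while treating values above 150 mEq/L as an outcome to be compared as a risk, and the sponsor should reconcile the two. Whether such infants, or those below 130, should be enrolled is for the trial team to decide. The point is worth acting on because the change to the analysis is cheap and uses a value the trial already collects.

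**What to change.** 1. State when the initial serum sodium is drawn: before allocation or, at the latest, before any study sodium.
2. Objective 1: analyse new-onset sodium below 130 mEq/L in later samples, among infants with initial sodium of at least 130.
3. Objective 2: analyse new-onset sodium above 150 mEq/L in later samples, among infants with initial sodium of at most 150.
4. Report the comparison of all randomised infants alongside each as supporting, with the number in each arm already abnormal at the initial sample.
5. If the initial sample cannot be placed before study sodium, do not restrict on it. Keep all randomised infants and describe the outcome as presence of the abnormality during the window, without a claim of prevention.

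The cost is a few sentences in Definitions and the analysis section, plus a fixed sampling time. Slightly fewer infants enter these two analyses, and their results do not apply to infants already abnormal at entry.

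### Simple randomisation and analyses that ignore gestational age leave the gestational-age mix of the arms to chance; stratifying and adjusting would be a cheap, modest gain

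*Combined protocol and SAP*

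**What the plan says.** Under Study design and statistical analysis, the combined protocol and SAP states that "The eligible patients will be simple randomized in two groups". It mentions no blocks, strata or minimisation. The Introduction places the trial in a single unit, for infants "admitted to the Newborn Intensive Care Unit at Children Hospital in Saltillo Coahuila Mexico". The eligibility criteria are "Preterm infants <35 weeks of gestation" and "Less than 24 hours of life", with four groups of malformations excluded and no lower limit on gestational age.

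The baseline data are described as follows: "At admission, gestational age and sex and birth weight will be recorded".

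The first objective is to "Compare the risk of hyponatremia in the first 72hrs of life" between early and late sodium intake. On analysis, "The risk of hyponatremia and hypernatremia will be expressed using relative risk", and "normally distributed data will be compared with t test or Chi squared test", with Mann-Whitney or Fisher tests as alternatives. Changes over time go to repeated measures ANOVA or Kruskal-Wallis. Gestational age appears in none of these analyses, either as a covariate or as a stratum. No sample size is stated.

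**The concern.** The population runs from the most immature infants admitted up to just under 35 weeks. Immaturity can be expected to bear on serum sodium, weight loss and the listed complications, although the documents give no event rates by gestational age. With simple randomisation, only trial size keeps the arms alike in this respect, and the documents do not give that size.

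The trial produces one realised allocation. If one arm happens to receive more of the most immature infants, the difference passes directly into the crude relative risks, because neither the allocation nor the analysis deals with it. What is at stake is precision and the credibility of the realised comparison. The factor is known before allocation, so dealing with it needs no new data.

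**Working it through.** The plan has no figure to reproduce: it states no sample size, event rate or allocation ratio. The inputs below are therefore assumptions, shown over a range.

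**Inputs.** From the documents: simple randomisation, two arms, gestational age known at allocation, no gestational-age term in any analysis. Assumed: 1:1 allocation; total N of 40, 60, 100 or 200; a share f of infants in the most immature band of 30% (also 20% and 50%); event risk 40% in that band and 10% elsewhere.

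**Step 1. Chance of a 15-point gap in mix.** Let M ~ Binomial(N, f) infants be in the immature band. Given M, arm 1 receives A ~ Binomial(M, 0.5) of them and B ~ Binomial(N − M, 0.5) of the others. The gap is d = |A/(A+B) − (M−A)/(N−A−B)|. Summing the exact probabilities of d ≥ 0.15 gives:

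| Total N | f = 20% | f = 30% | f = 50% |
|---|---|---|---|
| 40 | 25% | 32% | 36% |
| 60 | 15% | 21% | 25% |
| 100 | 6% | 10% | 14% |
| 200 | 0.8% | 2% | 3.5% |

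Hand check for f = 30%: the standard deviation of the signed gap is about √(0.3 × 0.7 × 4/N), which is 0.145, 0.118, 0.092 and 0.065. Then 0.15 is 1.04, 1.27, 1.64 and 2.31 standard deviations, and the two-sided normal tails are 30%, 20%, 10% and 2%.

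**Step 2. What a 15-point gap does.** The shift in the crude risk difference with no treatment effect is 0.15 × (0.40 − 0.10) = 0.045, or 4.5 points.

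**Step 3. That shift against sampling error.** Overall risk is 0.3 × 0.40 + 0.7 × 0.10 = 0.19, so the outcome variance is 0.19 × 0.81 = 0.1539. The standard error of the crude risk difference is √(4 × 0.1539/N): 12.4, 10.1 and 7.8 points at N = 40, 60 and 100. The shift is therefore 0.36, 0.44 and 0.57 standard errors.

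**Step 4. Gain from balancing and adjusting.** The part of the outcome variance that lies between bands is 0.3 × 0.7 × (0.40 − 0.10)² = 0.0189, and 0.0189/0.1539 = 12.3%. Removing it multiplies the standard error by √(1 − 0.123) = 0.937, a reduction of about 6%. With milder assumed risks of 40% and 20%, overall risk is 0.26, the variance is 0.26 × 0.74 = 0.1924, the between-band part is 0.3 × 0.7 × 0.04 = 0.0084 (4.4%), and the reduction is about 2%.

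**Step 5. Arm sizes.** The exact binomial chance of a split strictly worse than 40/60 is 15.4%, 9.2%, 3.5% and 0.4% at the four sizes. A 60:40 split keeps 4 × 0.6 × 0.4 = 96% of the efficiency of equal arms.

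**Step 6. Effect of stratified blocks.** In simulations with two strata and blocks of 4 (N = 40 to 200; f = 20%, 30%, 50%), the arms never differed by more than 4 infants and a 10-point gap in mix never occurred. Larger or varying blocks would balance slightly less tightly.

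**The case against.** The strongest reply is that nothing here is wrong. Simple randomisation is unbiased on average, does not inflate the type I error, and is the hardest scheme to predict. The usual confidence interval already allows for chance imbalance. A 4.5-point shift looks large only when shown without its standard error, and it is an upper-tail case: at N = 200, a gap big enough to produce it has about a 2% chance. Sodium change and weight change are also measured from each infant's own starting value, which removes baseline-level differences in those two outcomes. All of this stands, and it is why the point is graded as minor. Own-baseline differences do not, however, adjust for an effect of gestational age on the change itself or on the binary outcomes.

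A second reply is that a prespecified adjusted analysis would deal with the mix without making allocation more predictable. That also stands, and it is offered below as the fallback.

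A reader might infer three stronger points, which the documents do not support:

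- **Uneven arms as a serious cost.** Step 5 shows that they are not.
- **Complications too sparse for analysis to repair an imbalance.** The documents give no rates for necrotizing enterocolitis, intraventricular hemorrhage or death, and a Mantel-Haenszel estimate over two strata tolerates sparse cells.
- **An unmasked ward.** The documents do not say whether the trial is masked.

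**Conclusion.** The point holds as a cheap improvement. The plan leaves the gestational-age mix to chance at allocation and does not use gestational age in the analysis, although the variable is in hand. How often that matters depends on the unstated sample size: with 30% of infants in the most immature band, a gap of 15 points or more has about a one-in-three chance at 40 infants, one in ten at 100 and one in fifty at 200. The expected benefit is small: a standard error about 6% lower under risks of 40% and 10%, and about 2% lower under 40% and 20%. The band share, the event risks, the trial sizes and 1:1 allocation are all assumptions.

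It would be wrong to conclude that the trial is biased or its randomisation invalid. Severity: minor.

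**What to change.** Under Study design and statistical analysis, replace the simple randomisation statement with: *Eligible infants will be randomised 1:1 in permuted blocks of randomly varying size, stratified by gestational age in two bands, from a concealed list.* The investigators should choose and state the cut between bands.

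In the analysis text, prespecify the gestational-age stratum as a term in the hyponatremia, hypernatremia, serum sodium and weight analyses, and a Mantel-Haenszel stratified relative risk for sepsis, necrotizing enterocolitis, intraventricular hemorrhage and death.

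If the allocation scheme cannot be changed, keep simple randomisation and prespecify the gestational-age-adjusted analyses alone. That deals with the mix but not with arm sizes, which matter little.

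The cost is a regenerated allocation list and a few lines of analysis text; no new data are collected. The downside is that blocks are slightly more predictable than simple randomisation, which the varying block sizes and the concealed list limit.

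### Objectives 1 and 2 count abnormal sodium from birth to 72 hours, although study sodium may start only at 24 hours; a pre-start value counted as an event would pull the relative risk toward 1.

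*Combined protocol and SAP*

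**What the plan says.** **Outcome window.** Objective 1 is to "Compare the risk of hyponatremia in the first 72hrs of life, in preterm newborns with early sodium intake and late sodium intake". Objective 2 uses the same window: "Compare the risk of hypernatremia in the first 72hrs of life, in preterm newborns with early sodium intake and late sodium intake". The section Study design and statistical analysis repeats it: "The incidence of hyponatremia, hypernatremia, change of serum sodium and weight change will be evaluated and compared between groups during this time frame (72hrs".

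**Start of study sodium.** The Introduction gives 24 hours of life twice: "Hypothesis: early (24 hours of life) sodium supplementation (5mEq/kg/day) prevents the develop of hyponatremia in preterm infants" and "Infants receive at 24 hours of life; sodium (5mEq/kg/day) versus less than 1mEq/kg/day". The arm definition gives a day but no hour: "Intervention: Sodium administration, enteral and/or parenteral of 5mEq/kg/day starting on day of life one". The comparison arm has the same day-one wording.

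**Entry.** Infants qualify at "Less than 24 hours of life", and "The eligible patients will be simple randomized in two groups". No blinding is stated.

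**Samples and definitions.** Blood is drawn every 24 hours for 3 days. Hyponatremia (below 130 mEq/L) and hypernatremia (above 150 mEq/L) are bare thresholds. Sodium change is measured at 48 and 72 hours against an initial serum sodium that has no stated hour. Weight change is measured at 24, 48 and 72 hours against birth weight. The exclusion criteria do not mention sodium at entry, and no rule limits events to new cases or to samples drawn after the start.

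**The concern.** On the Introduction's timing, the first 24 of the 72 hours (one third of the window) come before study sodium. The contrast between the two change definitions suggests that the first sodium sample is a baseline: weight has a 24-hour follow-up value, sodium does not. The same sample would then be the reference for Objective 3 and a possible event for Objectives 1 and 2.

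The hypothesis is about prevention, and an abnormality already present at the start cannot be prevented. Such cases are expected equally often in both arms, so counting them adds the same amount to both risks and moves their ratio toward 1. For Objective 1 this hides benefit and costs power. For Objective 2, a safety comparison, it hides harm. Without a counting rule, the choice between a whole-window count and a post-start count could also be made after the data are seen.

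**Working it through.** **Inputs.** From the documents: the 72-hour window, the two start statements, the thresholds, relative risk as the effect measure, and significance at p < 0.05. The documents give no event rate, target effect, pre-start share or sample size, so there is no planned figure to reproduce. Assumed for illustration: 1:1 allocation, a two-sided test, and the rates below.

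**1. Relative risk as the plan counts.** Let b be the share abnormal on a pre-start sample, equal in expectation between arms. Let pL and pE be the later risks of a new abnormality (late and early arms) in infants normal at the start.

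Whole-window RR = [b + (1 − b)pE] / [b + (1 − b)pL]; RR for new post-start cases = pE / pL.

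For b > 0 and pE ≠ pL, the first always lies between the second and 1. At b = 5%, 20% versus 10%: (0.05 + 0.95 × 0.10) / (0.05 + 0.95 × 0.20) = 0.145 / 0.240 = 0.604.

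| Later risk, late vs early arm | b = 0 | 1% | 2% | 5% | 10% |
|---|---|---|---|---|---|
| Hyponatremia 10% vs 5% | 0.50 | 0.55 | 0.59 | 0.67 | 0.76 |
| Hyponatremia 20% vs 10% | 0.50 | 0.52 | 0.55 | 0.60 | 0.68 |
| Hyponatremia 40% vs 20% | 0.50 | 0.51 | 0.52 | 0.56 | 0.61 |
| Hypernatremia 5% vs 10% | 2.00 | 1.83 | 1.71 | 1.49 | 1.31 |

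**2. Post-start samples only, all randomized infants.** Let qL and qE be the shares of pre-start abnormalities still present on a later sample.

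RR = [b·qE + (1 − b)pE] / [b·qL + (1 − b)pL]. At b = 5%, 20% versus 10%:

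- equal persistence 50%: 0.120 / 0.215 = 0.558
- equal persistence 100%: 0.145 / 0.240 = 0.604
- 100% late, 50% early: 0.120 / 0.240 = 0.500

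**3. Power.** 200,000 simulated trials per setting, b = 5%, 20% versus 10%. Uncorrected chi-square for the first two rows; Cochran-Mantel-Haenszel test stratified by pre-start status, with the Mantel-Haenszel relative risk, for the rest.

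| Count | RR | Power, 200 per arm | Power, 50 per arm |
|---|---|---|---|
| Whole window, as written | 0.60 | 68% | 23% |
| New cases in infants normal at start | 0.50 | 79% | 28% |
| Post-start, all randomized, equal persistence 50% to 100% | 0.56 to 0.60 | 75% to 79% | 25% to 27% |
| Post-start, all randomized, persistence 100% late, 50% early | 0.50 | 92% | 36% |

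At b = 1% and 200 per arm, whole-window power is 78% against 80% for new cases.

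**4. Null check.** With 20% later risk in both arms and b = 5%, every method rejects in about 5% of trials.

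**The case against.** **The premise is unproven.** The arm definitions allow a start on the first day, and entry is before 24 hours, so the first sample may follow the start. The contrast between the sodium and weight definitions shows that the initial value is a reference, not that it precedes study sodium. This stands: the point is conditional.

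**The pull depends on the comparison.** The 0.50 applies to infants normal at the start. Among all randomized infants, if every early abnormality persists, dropping the first sample leaves the relative risk at 0.604. If study sodium acted on existing abnormalities in the opposite direction to its effect on new ones, counting the first sample could even move the ratio further from 1 than the all-infant post-start ratio. This also stands, so the comparator has to be named: new post-start cases, which is what the word prevents implies.

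**The size may be small.** At b = 1% the loss is slight, and at 50 per arm power is low under every count, so dilution is not the main limit there. True. But no document shows that b is that small, and the fix costs little.

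**Incidence may already mean new cases.** It may, but no rule says so.

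**Stronger readings that do not hold.** A reader might infer that the 72-hour comparison is invalid. It is not: it compares all randomized infants and keeps its type I error. A reader might also infer that only leaving out already abnormal infants can restore the relative risk. That requires early abnormalities to persist equally in both arms, which nothing in the documents supports. Leaving infants out also has a price: allocation may precede the first sample, so the exclusion may rest on a value taken after randomization.

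**Conclusion.** The concern holds conditionally and should be fixed. The outcome window opens at birth, the Introduction starts study sodium at 24 hours, and nothing sets earlier values aside. If the first sample precedes the start, the expected relative risk for new cases is pulled toward 1: from 0.50 to between 0.52 and 0.60 at an assumed b of 1% to 5% with risks of 20% versus 10%. At b = 5% and 200 per arm, power is 68% rather than 79%. A hypernatremia ratio of 2.00 would fall to between 1.83 and 1.49 over the same range of b, with risks of 10% early and 5% late.

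The true size is unknown, and it is zero if b = 0 or if the first sample follows the start. The statement concerns the expected ratio; chance imbalance can move a single trial either way. Confidence is medium, because the documents do not settle the sample timing.

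**What to change.** 1. Reconcile the 24-hour statements in the Introduction with the day-one wording of the arm definitions. This review takes no view on which is right.
2. Record when the allocated regimen starts, using the same anchor in both arms, and define the initial serum sodium as the last value before that time.
3. For the main analysis of Objectives 1 and 2, keep all randomized infants, count only samples drawn after the start, and stratify or adjust the relative risk by the initial sodium (for example, a Mantel-Haenszel relative risk).
4. Report two sensitivity analyses: new cases among infants free of that abnormality at the initial sample, with the number left out by arm; and the full 72-hours-of-life count in all randomized infants.

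**Cost.** A recorded time, some definition wording and slightly more analysis. No extra sample is needed if the first scheduled one precedes the start. If it follows the start, there is no value to set aside and the count needs no change. The new-case analysis would leave out about 10 of 200 infants per arm at b = 5%. It is safe only if care before the initial sample does not differ by arm, which is why it is not the main analysis and why the by-arm numbers are needed. The main analysis leaves nobody out, but its relative risk also depends on how existing abnormalities resolve in each arm, and the report should say so.

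### A normality check decides whether continuous outcomes are compared by means or by ranks, so the sample picks the question; one pre-specified baseline-adjusted analysis should replace it

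*Combined protocol and SAP*

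**What the plan says.** The section on study design and statistical analysis contains two data-driven switches for continuous outcomes.

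- Two-group comparisons: "The distribution of variables will be assessed with Shapiro Wilk test, normally distributed data will be compared with t test", and "those with abnormal distribution with Mann-Whitney U test or Fisher exact test".
- Changes over time in serum sodium, the other blood chemistry and weight: these "will be evaluated using repeated measures ANOVA or Kruskal-Wallis test depending on data distribution". The sodium and weight changes are objectives 3 and 4.

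An effect measure is fixed only for two binary outcomes: "The risk of hyponatremia and hypernatremia will be expressed using relative risk". For sodium change, the Definitions give the within-infant quantity, "The difference between serum sodium (at 48 and 72hrs) and initial serum sodium", but the plan names no between-group estimate or interval for this or any other continuous outcome. It does not give the significance level of the Shapiro-Wilk test. Nor does it say whether that test is applied per arm, to both arms together, at each time or to residuals. The general threshold is a p-value below 0.05.

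**The concern.** A t test compares means; Mann-Whitney compares ranks. Since the plan names no effect measure for continuous outcomes, the selected test is the only thing that defines what is compared, and the sample selects it. Two analysts could both follow the plan and report different analyses, because the details of the normality check are left open.

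The second switch matters more, because it governs objectives 3 and 4. Kruskal-Wallis is a rank comparison of independent groups. Applied to the two arms, it has no within-infant or time structure, so a failed normality check removes the repeated-measures analysis altogether. Applied across times, it would treat one infant's values as independent.

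At stake are the interpretability of the sodium and weight results and, in some circumstances, the error rate of a claim about mean change.

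**Working it through.** The plan has no sample size, power, SD or effect size, so there is no design figure to reproduce. The check is by simulation.

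**Inputs from the plan.** Two arms, simple randomization, Shapiro-Wilk choosing between t test and Mann-Whitney, threshold 0.05.

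**Assumptions.** Two-sided tests; Shapiro-Wilk at 0.05; 1:1 allocation unless stated; 20, 30 or 50 per arm; gamma data with skewness 1 unless stated; true mean difference zero. The two-stage rule is a pooled t test if normality passes and Mann-Whitney if it fails. The comparator is Welch's t test with no pre-test. With 4,000 trials per setting, the Monte Carlo error at 5% is about 1.96 × √(0.05 × 0.95 / 4,000) = 0.7 points.

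**Step 1: how often the test switches.** With normal data checked per arm, 1 − 0.95² = 9.75%; simulation gives 9% to 10% (about 5% if both arms are checked together). With skewness 1, one arm of 30 fails in 44.1% of trials, so at least one of two fails in 1 − 0.559² = 69%. The per-arm rule switches in about 50% of trials at 20 per arm and 90% at 50. The same population thus yields different tests.

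**Step 2: type I error for a mean difference, skewness 1.** Ranges are over repeated runs.

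| Per arm | SD ratio | Two-stage, checked per arm | Two-stage, arms checked together | Welch (per-arm runs) |
|---|---|---|---|---|
| 30 | 1 | 4.7–5.9% | 4.6% | 4.4–5.4% |
| 30 | 1.5 | 6.7–7.5% | 6.1% | 4.6–5.7% |
| 30 | 2 | 9.2–10.3% | 8.3% | 4.9–5.7% |
| 50 | 1.5 | 8.2–8.4% | not run | 5.1% |
| 50 | 2 | 12.1–13.0% | 10.8% | 4.8–5.7% |

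When both arms have the same distribution, the two-stage rate lies between 4.2% and 6.0% across normal, t with 5 degrees of freedom, gamma, lognormal and exponential data.

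**Step 3: where the excess comes from.** Take one run at 30 per arm and SD ratio 2. The overall rate is (share switched × Mann-Whitney rejections among them) + (share not switched × t rejections among them) = 0.6965 × 0.1181 + 0.3035 × 0.0667 = 0.0823 + 0.0202 = 10.25%. Most of it is the rank branch. In a further run, Mann-Whitney with no pre-test gave 8.5% at 30 per arm and 13.4% at 50, against 8.8% and 13.1% for the two-stage rule and 4.9% and 5.5% for Welch.

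**Step 4: sensitivity to the assumptions.** Normal data, equal arms, SD ratio 1.5 to 2: 4.9% to 6.3%, so unequal spread alone does little. Normal data with 25 versus 35 infants and double the SD in the smaller arm: 7.7% to 8.7% against 4.7% to 5.1% for Welch; here the pooled t test is the cause. Heavier skew at SD ratio 2: lognormal(0.5) gives 13.9% to 15.0% at 30 per arm and 20.5% to 21.2% at 50; exponential gives about 25% at 30.

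**Step 5: power of the replacement.** With equal SDs and a true difference of 0.6 SD, two-stage against Welch at skewness 1 is 69% v 64% (30 per arm) and 88% v 84% (50). For lognormal(0.5) it is 79% v 65% and 95% v 85%. So Welch alone costs power under skew. Baseline adjustment reverses this. If baseline and follow-up have equal variance and correlation ρ, the residual variance of the adjusted model relative to a change score is (1 − ρ²) / (2(1 − ρ)) = (1 + ρ)/2, which is 0.65, 0.75 and 0.85 for ρ = 0.3, 0.5 and 0.7. Simulated power with skewed data and 30 per arm was 64%, 74% and 88% for the adjusted model, against 51%, 66% and 86% for the two-stage test on change scores. Type I error of the adjusted model was 4% to 5%.

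These runs cover t test against Mann-Whitney at a single time. No rate was computed for the ANOVA/Kruskal-Wallis switch. With two arms at one time its rank branch is in essence the Mann-Whitney test, but its ANOVA branch was not simulated.

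**The case against.** The strongest reply is that the normality check is not itself the source of the inflation. A fully pre-specified Mann-Whitney gives the same figures, and its rejections count as false only if the target is a mean difference, which the plan never states. The inflation also needs skew together with unequal spread, or unequal spread together with unequal arms, and nothing in the documents shows that either holds. All of this stands. It leaves untouched the point that the sample chooses the hypothesis, and the missing statement of a target is part of the defect.

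A reader might infer more than the documents support:

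- *That the main result is at risk.* The stated hypothesis concerns hyponatremia, a binary outcome reported as a relative risk. The sentence does tie the chi-squared and Fisher tests to distribution, which makes no sense for binary data, but the relative risks do not depend on it.
- *That one fixed method is at least as good in every setting.* Step 5 shows that Welch loses power under skew with equal spread.
- *That ranks can yield only a p-value.* A Hodges-Lehmann shift with an interval is available. The plan names no estimate for the t test branch either.
- *That sodium change has a 26% chance of at least one switch with normal data.* That figure takes six checks (two arms, three times): 1 − 0.95⁶ = 26%. Sodium change is defined at two times, so four checks give 1 − 0.95⁴ = 18.5%, and even that presumes separate checks by arm and time, which the plan does not describe.

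**Conclusion.** The point holds as a modest weakness. Both switches are in the plan, and nothing elsewhere fixes one analysis for any continuous outcome. For objectives 3 and 4 the sample decides whether mean change or ranks are compared, and whether the repeated-measures structure is kept. That needs no assumption about the data.

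The effect on error is conditional. It is near 5% when the arms share a distribution. As a test of a mean difference it is about 7% to 13% at skewness 1, SD ratio 1.5 to 2 and 30 to 50 per arm with the check made per arm (6.1% to 10.8% in the settings run with the arms checked together), and higher with heavier skew. The excess at equal arm sizes is due mainly to Mann-Whitney serving as a test of means. Unequal spread is conceivable when the arms differ several-fold in sodium intake, but the documents give no SDs, sample size or distributions, so no particular inflation can be attributed to this trial.

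**What to change.** Delete the normality check for continuous outcomes and pre-specify one analysis: a linear model, or a repeated-measures mixed model, of the follow-up value on arm, with the baseline value (initial serum sodium, birth weight, or the first value of the other chemistry) as covariate. Report the mean difference with 95% CI and robust standard errors, so that unequal spread or unequal arms do not distort it. State that the initial sample precedes the assigned intake, since only then is it a baseline. Use Welch's t test where no baseline exists. Keep the rank tests as labelled sensitivity analyses.

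The cost is wording: baseline values are already collected and the models are standard. The gain from adjustment shrinks as the baseline correlation nears 1, so it may be small for weight. Where there is no baseline, Welch gives up about 4 to 6 points of power against the present rule at skewness 1 with equal spread, and 10 to 14 points in the lognormal settings above.
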